11.3 Secondary Efficacy Analysis

All Phases:

- **To assess tumor response to treatment**

11.3.1 Tumor Response-related Variables

- Investigator determined tumor response assessment

Investigator determined tumor assessments will be performed at baseline and at 8-week intervals following initiation of MM-398. Overall tumor response for post-baseline assessments will be classified as Complete Response (CR), Partial Response (PR), Stable Disease (SD), Progressive

Disease (PD), Not Evaluable (NE) or Non-CR/Non-PD (no-target disease only) per RECIST version 1.1 criteria or modified RECIST criteria for cohort 3 CNS disease only.

For each tumor assessment, investigators will evaluate and report on the CRF a classification of overall tumor response and its components (target lesions, non-target lesions, and new lesions). Main analyses of tumor response related variables will be based on the investigator assessment of tumor response.

Derived efficacy evaluations including progression-free survival, best overall response, and objective response rate will be based on investigator determined tumor response data.

- Radiological tumor response assessment

In addition to investigator determined tumor response assessment, tumor that have FMX uptake measurement will also be measured radiologically in central facility. Response classifications will be algorithmically computed from the data on target lesions, non-target lesions and new lesions. The radiological tumor response will be reported separately for associating with ferumoxytol (FMX) uptake.

11.3.2 Secondary efficacy variables (All Phases)

Secondary efficacy analysis will be based on Investigator determined tumor response assessment following RECIST 1.1. Cohort 3 CNS disease will be analyzed according to RECIST and modified RECIST, separately. The worst case between RECIST and modified RECIST may be reported.

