Tumor evaluation will be measured according to Response Evaluation Criteria In Solid Tumors (RECIST) version 1.1 for non-CNS disease, or according to modified RECIST criteria as defined in this protocol for CNS disease. Tumor evaluations will be characterized according to best overall response (BOR), duration of response (DOR), progression-free survival (PFS), and clinical benefit rate (CR, PR, or SD \geq 24 weeks). Objective response rate (ORR) and BOR will be summarized using frequency and percentage. PFS will be described using Kaplan-Meier methods.
FMX uptake will be summarized as a continuous parameter. Box and whisker plots will be displayed for FMX uptake. The relationship between FMX uptake and tumor response will be evaluated using various parameters and methods. Relationships may be explored as appropriate. Additionally, informal Fisher's exact test will be used to investigate dichotomous FMX cut-points as related to ORR. Other graphical procedures may be implemented to explore the relationship between FMX and efficacy response.
 Spearman pairwise correlations will be computed between the following measurements: FeMRI levels Tumor associated macrophage levels Tumor irinotecan levels Tumor SN-38 levels
Graphical and regression methods will be used to explore potential relationships among correlated measurements. In addition, relationships between

	pharmacodynamics markers and efficacy response will be evaluated in an exploratory manner.
	PK parameters will be derived from the blood PK samples and will be analyzed using descriptive statistics, including the median, mean and 95% confidence intervals around parameter estimates by dose level. All PK parameters will include Cmax, Tmax, AUC (area under the concentration curve), clearance, volume of distribution at steady state (Vdss), and the terminal elimination half-life. Estimation of the pharmacokinetic parameters will be performed using standard non-compartmental methods.
Sample Size Justification	No formal hypothesis testing will be performed for this study. The Pilot Phase will enroll 12-20 patients in a variety of indications, while the Expansion Phase will enroll approximately 30 patients with metastatic breast cancer within 3 cohorts. Although no formal sample size calculation was performed for either study phase, the anticipated response rate in the HER2 negative Expansion Phase is estimated around 29% [36].

2 Background Information and Rationale

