- g) Normal ECG or ECG without any clinically significant findings
- h) Recovered from the effects of any prior surgery, radiotherapy or other anti-neoplastic therapy
- i) At least 18 years of age
- j) Able to understand and sign an informed consent (or have a legal representative who is able to do so)

Expansion Phase additional inclusion criteria:

- k) Received at least one cytotoxic therapy in the metastatic setting, with exception of TNBC patients who progressed within 12 months of adjuvant therapy
- Received ≤ 5 prior lines of chemotherapy in the metastatic setting (no limit to prior lines of hormonal therapy in Cohort 1)
- m) Candidate for chemotherapy
- n) At least one lesion amenable to multiple pass biopsy (exception: Cohort 3 patients)

Expansion Phase Cohort 3 additional inclusion criteria:

- o) Radiographic evidence of new or progressive brain metastases after prior radiation therapy with at least one brain metastasis measuring ≥ 1 cm in longest diameter on gadoliniumenhanced MRI (note: progressive brain lesions are not required to meet RECIST criteria in order to be eligible; extra-cranial metastatic disease is also allowed)
- p) Imaging following prior radiation is not consistent with pseudo-progression in the judgment of treating clinician
- q) Neurologically stable as defined by:
 - Stable or decreasing dose of steroids and anti-convulsants for at least 7 days prior to study entry
 - No clinically significant mass effect, hemorrhage, midline shift, or impending herniation on baseline brain imaging
 - No significant focal neurologic signs and/or symptoms which would necessitate radiation therapy or surgical decompression in the judgment of the treating clinician
- r) No evidence of diffuse leptomeningeal disease on brain MRI or by previously documented cerebrospinal fluid (CSF) cytology-NOTE: discrete dural metastases are permitted.

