7.1.6 Disease Evaluation

Tumor response will be evaluated according to the Response Evaluation Criteria in Solid Tumors (RECIST) version 1.1 or modified RECIST criteria (for CNS disease only; Cohort 3), to establish disease progression by computed tomography (CT) or MRI. At baseline, all Expansion Phase patients with extracranial disease will also have a standard fluorodeoxyglucose (¹⁸F-FDG) positron emission tomography (PET)/CT scan in order to identify lesions that are metabolically active; follow-up PET/CT scans are not required. In addition, other radiographic or scintigraphic procedures (such as radionuclide bone scans), as deemed appropriate by the Investigator, will be performed to assess sites of neoplastic involvement. The same method of assessment must be used throughout the study. Patients in Cohort 3 with both CNS and non-CNS disease will have separate evaluations of each disease type. Investigators should select target and non-target lesions in accordance with RECIST v1.1 guidelines, or modified RECIST criteria as specified below for brain lesions. Follow up measurements and overall response should also be in accordance with these guidelines, unless otherwise specified below (Cohort 3 only).

7.1.6.1 Modified RECIST Criteria for Cohort 3

Tumor response for CNS disease will be evaluated according to modified RECIST criteria as described previously [37], and as specified below. A maximum of five target lesions (\geq 5 mm in size of long axis, with at least one lesion measuring \geq 1 cm) will be identified at baseline, with the remaining lesions followed as non-target lesions. Selection of necrotic or cystic lesions as target lesions should be avoided if other solid lesions are present. All target lesions should be measured for each follow-up disease evaluation, even if lesion size decreases to < 5 mm. If a lesion is too small to measure, a default value of 3 mm should be used. Table 12 describes the definition of response for CNS disease only; non-CNS disease will be assessed separately according to RECIST v1.1.

Response	Definition
Complete Response (CR)	Disappearance of all target and non-target lesions; or lesions do not show
	any gadolinium enhancement and are completely necrotic
Partial Response (PR)	\geq 30% decrease in the sum longest dimension (LD) of target lesions
	(taking as reference
	the baseline sum diameters) and an absolute decrease of at least 5 mm in at

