10.6 Efficacy Analysis

Tumor evaluation will be measured according to Response Evaluation Criteria In Solid Tumors (RECIST) version 1.1 (Cohort 1 and 2, and non-CNS disease for Cohort 3) or modified RECIST

as defined in section 7.1.6.1 (CNS disease; Cohort 3 only). Best Overall Response (BOR) is defined as the best response as recorded from the start of MM-398 until disease progression.

Objective Response Rate (ORR) is defined as the proportion of patients with a BOR characterized as either a Complete Response (CR) or Partial Response (PR) relative to the total number of evaluable patients. Exact 95% confidence intervals based on the binomial distribution will be reported.

Clinical benefit rate is defined as the proportion of patients with a BOR characterized as a CR, PR, or Stable Disease (SD) \geq 24 weeks. Proportion of patients relative to the total number of evaluable patients will be reported with exact 95% confidence intervals based on the binomial distribution.

Duration of Response (DR) is defined as the time from first documentation of response (CR or PR whichever occurs first) to the date of disease progression or to death due to any cause, whichever occurs first.

Progression-free survival (PFS) is defined as the time from first dose of MM-398 to the date of radiologic disease progression by RECIST per Investigator or death due to any cause, whichever occurs first. Rules for declaring PFS events versus censors will be described in the SAP.

A waterfall plot will be used to display BOR with maximum percent decrease in target lesion and FMX uptake value at 24 hours.

FMX uptake (ug/mL and/or %ID/kg) will be summarized as a continuous parameter. Absolute and change from baseline will be summarized. The number of target lesions decreasing, staying the same, increasing relative to FMX uptake with various thresholds will be summarized by frequency and percent according to cycle. Box and whisker plots will be displayed for FMX uptake by time point. The relationship between FMX uptake at 1-4 hours and/or 24 hours with tumor response will be evaluated using various parameters and methods. Relationships may be explored as appropriate. Additionally, informal Fisher's exact test will be used to investigate dichotomous FMX cutpoints as related to ORR. Other graphical procedures may be implemented to explore the relationship between FMX and efficacy response.

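### The SAP scores Cohort 3 brain disease by two criteria with an optional worst case, where the protocol names one, so the Cohort 3 ORR and CBR are not fixed

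*SAP*

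**What the plan says.** **Protocol.** Section 7.1.6.1 states: "Tumor response for CNS disease will be evaluated according to modified RECIST criteria as described previously [37], and as specified below". Table 12 then defines the response categories for brain disease, and the same section adds that "non-CNS disease will be assessed separately according to RECIST v1.1". The synopsis also specifies "modified RECIST criteria as defined in this protocol for CNS disease". Section 10.6 repeats the split: RECIST 1.1 for Cohorts 1 and 2 and for non-CNS disease in Cohort 3, and modified RECIST "as defined in section 7.1.6.1 (CNS disease; Cohort 3 only").

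**SAP 11.3.1** agrees: RECIST 1.1 in general, and "modified RECIST criteria for cohort 3 CNS disease only".

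**SAP 11.3.2** does not. It first bases the secondary analysis on investigator assessment under RECIST 1.1. It continues: "Cohort 3 CNS disease will be analyzed according to RECIST and modified RECIST, separately". It ends: "The worst case between RECIST and modified RECIST may be reported".

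**The endpoint definitions that follow in the SAP** differ from one another:
- PFS (11.3.2.1) uses RECIST, or modified RECIST for Cohort 3 brain disease.
- Best overall response (BOR, 11.3.2.2) refers to RECIST only.
- ORR and CBR (11.3.2.3 and 11.3.2.4) are built on BOR. Their denominator is treated patients whose disease was measurable at baseline, with no criterion named.

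**The concern.** Two SAP sections one heading apart give different rules for the same lesions, and the second departs from the protocol without presenting itself as a change. Two separate analyses can sit side by side in a Cohort 3 table, but the overall Expansion Phase row can take only one classification per patient, and the SAP does not say which. Read literally, the BOR definition puts RECIST there, while the protocol puts Table 12 there for brain disease. The worst-case sentence adds a third possible result, with no statement of when it is shown or what worst means for each endpoint.

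ORR and CBR are the efficacy indicators named in the Expansion Phase secondary objectives, and Cohort 3 is 10 of the planned 30 patients. The study is open label (SAP 3.3), and data may be looked at administratively while it runs (SAP 5.1). The choice could therefore be settled after the results are known.

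**Working it through.** **1. The plan's own ORR figures.** SAP section 4 takes a true ORR of 30% and n = 30. The exact binomial tail is P(X ≥ r) = Σ C(30,k) 0.3^k 0.7^(30−k), summed over k = r to 30.
- r = 14: 0.0401, stated as 0.04.
- r = 13: 0.0845, stated as 0.084.

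Both reproduce. This point does not dispute them.

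**2. Criterion for Cohort 3 brain disease, place by place.**

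| Place | Criterion for brain disease |
|---|---|
| Protocol synopsis, 7.1.6.1, 10.6 | Modified RECIST |
| SAP 11.3.1 | Modified RECIST |
| SAP 11.3.2 | RECIST and modified RECIST, with optional worst case |
| SAP 11.3.2.1 (PFS) | Modified RECIST, on the natural reading |
| SAP 11.3.2.2 (BOR, hence ORR and CBR) | RECIST; modified RECIST not mentioned |

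The conflict is confined to the general rule in 11.3.2 and to the BOR family of endpoints.

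**3. Direction of a worst case.** If worst is taken patient by patient, a patient responds only if both criteria say so, so the count cannot exceed either separate count. If worst is taken on the summary, it is the smaller of two rates. In both cases ORR and CBR cannot rise. For PFS, the earlier of two progression dates cannot be later than either. Duration of response (DOR) has no such guarantee: a stricter rule can remove responders and leave a longer median.

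**4. Effect of one patient classified differently.** Sizes are 10 per cohort and 30 in the Expansion Phase, assuming all are evaluable. Intervals are exact (Clopper-Pearson) 95%.
- Cohort 3: 1/10 = 10 points. For example, 3/10 = 30% (6.7 to 65.2) becomes 2/10 = 20% (2.5 to 55.6).
- Expansion Phase: 1/30 = 3.3 points. For example, 9/30 = 30.0% (14.7 to 49.4) becomes 8/30 = 26.7% (12.3 to 45.9).

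**5. How often might the criteria disagree?** The documents give no rate. For an assumed per-patient rate q, the chance that at least one of 10 patients differs is 1 − (1 − q)^10.

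| Assumed q | Chance of at least one of 10 |
|---|---|
| 5% | 40% |
| 10% | 65% |
| 20% | 89% |
| 30% | 97% |

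**6. Where a disagreement could arise.** For partial response, Table 12 needs a fall of at least 30% in the sum and at least 5 mm in one target lesion. The RECIST 1.1 text is not in the documents, so a comparator with only the 30% condition is an assumption. For a single target lesion of length L, the two rules can part when 0.30 × L < 5 mm, that is L < 5/0.30 = 16.7 mm. Cohort 3 entry starts at 1 cm. A 10 mm lesion that shrinks by 3 mm meets the 30% rule and fails Table 12. Table 12 is the stricter rule here, so the worst case would equal the protocol's own result.

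**The case against.** The strongest reply is that little turns on this. Both separate analyses are mandatory and only the worst-case summary is optional. That summary cannot flatter the drug on ORR, CBR or PFS. The endpoints are secondary and descriptive, and no hypothesis is tested. The primary analysis of ferumoxytol uptake uses change in lesion size. Protocol 10.3 lets the SAP modify the planned analysis. All of this stands, and it limits the weight of the point.

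A second reply is that 11.3.2 is a badly worded combining rule: brain disease by modified RECIST, other disease by RECIST, and the worse of the two as the patient's overall response. That is plausible given SAP 11.3.1 and the PFS definition. It is not what the sentence says, since the sentence applies both criteria to brain disease, so it would need rewriting in any case.

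Three stronger readings are tempting, and the documents do not support them:
- *The sponsor could pick whichever criterion favours the drug.* Both analyses must be done, and the optional addition can only be unfavourable or neutral on ORR, CBR and PFS.
- *RECIST scoring is invalid for some eligible patients.* Protocol 5.1 says that "progressive brain lesions are not required to meet RECIST criteria in order to be eligible", but this may concern proof of progression rather than measurability, and a brain metastasis of at least 1 cm is required. What remains is that the SAP names no criterion for measurable disease in the denominator.
- *PFS is equally open.* Its own definition largely follows the protocol's split.

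**Conclusion.** The point holds as a conflict between stated rules. SAP 11.3.2 disagrees with the protocol and with SAP 11.3.1, and the RECIST-only definition of BOR leaves unsettled which result is the Cohort 3 ORR or CBR. It should be corrected before database lock. No type I error, power or sample size is affected, and no bias in the drug's favour has been shown.

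The size is 10 points on Cohort 3 ORR and 3.3 points on Expansion Phase ORR for each reclassified patient, if 10 and 30 patients are evaluable. How many patients would be reclassified cannot be derived from the documents. The 40% to 97% range rests on assumed disagreement rates of 5% to 30%, and the 16.7 mm threshold rests on an assumed 30%-only comparator and a single target lesion.

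**What to change.** **Bring the SAP back to the protocol.**
- In 11.3.2, replace the dual-criterion sentence so that Cohort 3 brain disease is scored by Table 12 and non-CNS disease by RECIST 1.1.
- Delete the optional worst-case sentence.
- If RECIST 1.1 scoring of brain lesions is still wanted, make it a labelled sensitivity analysis that is always reported.
- Align the BOR, ORR, CBR and DOR wording with this split.

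**Add what neither document contains.** These are new rules, not a restoration of the protocol.
- State one patient-level rule for combining CNS and non-CNS response, used for the Cohort 3 and overall rows. It must cover every response category: a rule for progression alone leaves, for example, partial response in the brain with stable disease elsewhere undefined. The need is practical, because protocol 7.1.6.2 allows treatment to continue after non-CNS progression while BOR stops at progression.
- Say which criterion defines measurable disease in the ORR and CBR denominators.

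The cost is SAP wording before database lock. Protocol 7.1.6 already calls for separate evaluation of the two disease types in these patients.

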11.3.2.1 Progression-Free Survival (PFS)

PFS is defined as the time in months from first dose of MM-398 to the date of radiologic disease progression by RECIST or mRECIST (cohort 3 CNS disease) per Investigator assessment or death due to any cause, whichever occurs first.

Date of Progression: the earliest date that an overall tumor response of PD or death is recorded. Data handling conventions for determining the date of progression are outlined in [Table 3](#).

If progression is associated with a new lesion, the date of progression is the date when the new lesion was detected, where progression is associated with the sum of target lesions and different lesions are measured on different dates in a given visit, use the earliest date for visit as the date of progression.

For patients who do not have qualifying progressive disease or death, the date of censoring for PFS is the date when the last valid tumor assessment determined a lack of progression. If the last valid tumor assessment involves measurements over multiple days in a visit, the date of the last measurement will be the censoring date. A tumor assessment is considered valid if data has been recorded for all target lesions and absence of new lesions is documented. Date of last non-PD/non-NE assessment is the date of first dose date for patients without a valid post-baseline tumor assessment.

Table 3 Data handling rules for PFS analysis

Condition	Date of Progression or Censoring	Event
No baseline tumor assessments	Date of first dose of MM-398	Censored
Progression documented within 12 weeks* of baseline or the last non-PD/non-NE tumor assessment	Earliest of: 
 • date of radiographic assessment showing new lesion (if progression based on new lesion) or • date of radiographic assessment of target/non-target lesions in which progression is documented 	Progression
Death within 12 weeks* of last non-PD tumor assessment without documented progression	Date of death	Progression
Death or first documented progression after 12 weeks* from last non-PD tumor assessment	Date of last non-PD assessment	Censored
None of the following: 
 • documented progression • death • treatment termination • New anticancer therapy started • cancer-related surgery 	Date of last non-PD assessment	Censored
Treatment termination for clinical deterioration without documented progression or death	Date of last non-PD assessment or date of first dose of study drug MM-398 if no evaluable post-dose tumor assessment	Censored
Treatment termination for adverse event or other reason without documented progression or death	Date of last non-PD assessment or date of first dose of study drug MM-398 if no evaluable post-dose tumor assessment	Censored
New anticancer therapy started prior to treatment termination without documented progression	Date of last non-PD assessment prior to start of new anticancer therapy or date of first dose of study drug MM-398 if no evaluable post-dose tumor assessment	Censored
Cancer-related surgery prior to documented progression	Date of last non-PD assessment prior to cancer related surgery or date of first dose of study drug MM-398 if no evaluable post-dose tumor assessment	Censored

*16 weeks will be used for PFS sensitivity analysis

As a sensitivity analysis, PFS will also be analyzed following the same censoring rule in table 3 with 16 weeks of baseline or the last non-PD/non-NE tumor assessment time window being applied.

Progression-Free Survival (PFS) will be presented for each cohort and overall for expansion phase.

PFS assessed by investigator will be analysed using Kaplan-Meier method and descriptively summarized at 3 months interval for each dose level cohort. Median PFS time and corresponding 95% confidence limits will be presented.

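### PFS Table 3 censors any progression first seen at the scheduled scan after a missed one, no planned analysis shows the effect of that rule, and its rows use different clocks

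*SAP*

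**What the plan says.** SAP 11.3.2.1 defines PFS from first dose of MM-398 to radiologic progression "per Investigator assessment or death due to any cause, whichever occurs first", and sends the reader to Table 3 for data handling. Three rows matter:

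- **Progression counted as an event:** "Progression documented within 12 weeks* of baseline or the last non-PD/non-NE tumor assessment".
- **Death counted as an event:** "Death within 12 weeks* of last non-PD tumor assessment without documented progression".
- **Censored at the last non-PD assessment:** "Death or first documented progression after 12 weeks* from last non-PD tumor assessment".

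The text above the table says that, without a qualifying event, "the date of censoring for PFS is the date when the last valid tumor assessment determined a lack of progression". It adds: "A tumor assessment is considered valid if data has been recorded for all target lesions and absence of new lesions is documented". It also gives a default: "Date of last non-PD/non-NE assessment is the date of first dose date for patients without a valid post-baseline tumor assessment".

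The single PFS sensitivity analysis keeps the same rules "with 16 weeks of baseline or the last non-PD/non-NE tumor assessment time window being applied".

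The scan schedule is in SAP 11.3.1 (8-week intervals from the start of MM-398) and in the Protocol 8.2 footnotes (±7 days, anchored to first dose). Protocol 10.6 leaves the event and censoring rules to the SAP. SAP 11.3.2.5 applies the PFS censoring rules to duration of response (DOR) for responders who neither progress nor die.

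**The concern.** A 12-week limit on an 8-week schedule leaves no room for one missed scan. A progression that is in the database, with a date, becomes a censored observation at the earlier scan or at first dose. The sensitivity analysis applies the same logic with a cut-off that sits exactly on the nominal gap after one missed scan, so a day or two of permitted scan timing decides between event and censoring. A reader therefore cannot see from the planned output what the gap rule does to the curve.

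Separately, the rows disagree on whether a not-evaluable (NE) scan restarts the clock. NE is a response category in SAP 11.3.1, so the case can arise. PFS is reported by cohort, with about 10 patients in each, so a single patient classified differently by two programmers would be visible.

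**Working it through.** **Inputs.** Scan k falls on day 56k ± 7 from first dose (SAP 11.3.1; Protocol 8.2). The main limit is 12 weeks = 84 days and the sensitivity limit 16 weeks = 112 days (Table 3). Months = (days + 1)/(365.25/12) (SAP 7.6.4.1). The plan gives no figure of its own for this rule, so there is none to reproduce.

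**1. Gap to the next scheduled scan.** Let a and b be the deviations of the later and the earlier scan, each from −7 to +7 days.

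- No scan missed: 56 + a − b = 42 to 70 days. Counted.
- One missed: 112 + a − b = 98 to 126 days. Of 15 × 15 = 225 day pairs, none is ≤ 84.
- First scan missed, counted from first dose: 112 ± 7 = 105 to 119 days. Never ≤ 84.
- Two missed: 168 + a − b = 154 to 182 days. Beyond both limits.

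This covers scheduled scans only. Deaths, unscheduled scans and the 30-day follow-up evaluation can still fall within 84 days. For example, with last dose on day 98 and the week-16 scan missed, follow-up on day 121 to 135 is 121 − 63 = 58 to 135 − 49 = 86 days after the week-8 scan.

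**2. What 16 weeks restores.** The share of one-missed-scan gaps ≤ 112 days depends on scan timing, which the documents do not give:

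- uniform over ±7 days: 120/225 = 53.3%
- the same, with the later scan shifted one day later: 105/225 = 46.7%
- uniform over ±3, ±2 or ±1 days: 57.1%, 60.0%, 66.7%
- every scan exactly on its day: 100%

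**3. The clock after an NE scan.** Take stable disease on day 56, NE on day 112 and progression on day 168.

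- From the last non-PD/non-NE scan: 168 − 56 = 112 days, so the progression row does not apply.
- From the last non-PD scan, read literally: 168 − 112 = 56 days, so the late-event row does not apply either.
- The text's clock gives censoring at (56 + 1)/30.4375 = 1.87 months. Using the other rows' non-PD clock for progression would give an event at (168 + 1)/30.4375 = 5.55 months.

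Now suppose this patient has no documented progression and dies on day 182. The death is 182 − 112 = 70 days after the NE scan, so the death row as worded gives an event at 183/30.4375 = 6.01 months. It is 182 − 56 = 126 days after the last evaluable scan, so the text's clock gives censoring at 1.87 months.

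**4. Baseline or first dose.** The screening evaluation may be up to 28 days before ferumoxytol, and first dose up to 7 days after it, so 35 days in total. An on-schedule first scan (day 49 to 63) can then be up to 63 + 35 = 98 days after baseline, which is over 84, though it is always within 84 days of first dose.

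**5. DOR.** Take a partial response on day 56, week 16 missed and progression on day 168. PFS is censored at 1.87 months. DOR is an event at (168 − 56 + 1) × 12/365.25 = 3.71 months if progression simply counts, or censored at 56 − 56 + 1 = 1 day if the PFS gap rule carries over.

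**6. Possible size.** A simulation used 40,000 patients per scenario. All rates are assumptions: exponential PFS with median 2, 3, 4 or 6 months; scan days uniform within ±7; follow-up of six months for everyone, or six months plus up to 12 or 24 months of uniform accrual (cut-off as in SAP 5.2). Deaths, unscheduled scans and 30-day scans are not modelled, so the shares are upper-end. Share of documented progressions censored:

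| Scans missed | 12-week | 16-week | 18-week |
|---|---|---|---|
| 5% at random | 6–8% | 3–4% | 0.2–0.5% |
| 10% at random | 13–16% | 7–9% | 1–2% |
| 20% at random | 24–31% | 13–19% | 3–8% |
| 5% before progression, 20–30% after | 17–31% | 9–19% | 2–9% |

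In 30 patients, the 12-week rule would censor about 1–2, 2–4 or 3–8 documented progressions at the three random rates. Compared with counting all events (12 or 24 months of accrual), 6-month PFS moves by −0.6 to +5.5 points, against a standard error of about 8–9 points at n = 30. The Kaplan-Meier median moves by 0.2 months or less in 18 of 20 scenarios for each accrual time. The other two, both with a true median of 6 months, move by about +1.7 months, a step of one scan interval.

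**The case against.** The strongest reply is that the 12-week rule is a choice the SAP may make. Protocol 10.6 delegates it, and SAP 11.3.2.1 ties the progression date to Table 3 where PFS is defined. That stands, and the main rule need not change. Delegation does not, however, supply an analysis that shows what the rule does.

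Sixteen weeks is two nominal scan intervals and restores every one-missed-scan progression if scans fall exactly on their days. That is true, but the protocol allows ±7 days and the result is sensitive to them.

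On the clock, the text above the table and the sensitivity sentence do point to non-PD/non-NE, and no row literally yields the 5.55-month event. The day-182 death also requires the week-24 scan, due by day 175, to be missed or not evaluable. Both criticisms are fair, but the conflict remains without that second gap. A death on day 150, before the week-24 window opens on day 161, is 150 − 112 = 38 days after the NE scan and 150 − 56 = 94 days after the last evaluable one. It is an event by the death row and censored by the text.

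The DOR point is weaker: the section can be read as inheriting Table 3, so it is missing detail rather than contradiction. Finally, the endpoints are descriptive, data left out of tables still appear in listings, and post-hoc analyses are allowed. This limits the severity but does not remove the conflict between the rows.

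**Conclusion.** The concern holds. The calendar result is exact for scheduled scans: after one missed scan, progression at the next is always censored in the main analysis, and the sensitivity analysis restores a share set by scan timing (all if scans are exactly on their days, 47–67% under the other timings tried). After two missed scans it restores none. Table 3 contradicts the text on whether an NE scan restarts the clock, and progression after an NE scan fits neither the progression row nor the late-event row.

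The practical size is minor to moderate. PFS and DOR are secondary and untested, the direction of bias is not fixed, and the number of patients affected rests entirely on assumed missed-scan rates. The change should be made because the rule as written is ambiguous and correcting it is cheap, not because the trial's conclusions depend on it.

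**What to change.** 1. Add one PFS sensitivity analysis that counts every documented progression and death at its recorded date, whatever the gap. Keep the existing censoring for new anticancer therapy and cancer-related surgery, and say so.
2. Use one clock start and one censoring date in every row of Table 3: the last valid non-PD/non-NE assessment, or first dose of MM-398 if there is none.
3. State in SAP 11.3.2.5 whether progression or death after a missed scan is an event for DOR.
4. Optionally, widen the sensitivity window to 18 weeks (126 days). This covers every one-missed-scan gap and excludes two, but only once item 2 is adopted, because a gap counted from baseline can reach 119 + 35 = 154 days. It matters less once item 1 is in place.

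The 12-week main rule can stay. The cost is rewording a few table rows, one sentence on DOR and one more Kaplan-Meier output, with no new data. The drawback of item 1 is that events after a missed scan are dated at detection, up to about one scan interval late.
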